Cover Page

Date: 3/20/2023

NCT05190120

Brief Title: Effect of Adductor Canal Block Versus Femoral Block on Pain and Quadriceps Strength

Official Title: Effects of Ultrasound-guided Adductor Canal Block Versus Femoral Nerve Block on Pain and Quadriceps Strength After Ambulatory Knee Arthroscopic Surgery

Study Protocol/Design

Patients undergoing arthroscopic knee surgery (ACL and non-ACL surgery) typically receive an ultrasound-guided femoral nerve block or an adductor canal block in the pre-operative phase for post-operative pain control. While an effective method for post-operative analgesia, the femoral nerve block is associated with profound quadriceps weakness for the duration of the nerve block, which can impair ambulation, rehabilitation, and increase the risk of falls. The more distal adductor canal block, however, contains primarily sensory branches of the femoral nerve and has been purported by small volunteer studies to provide equally effective analgesia with minimal motor block and quadriceps weakness (as compared to femoral nerve block). We will prospectively randomize patients undergoing knee arthroscopy at the UCSF Orthopaedic Institute to receive either a single-shot femoral nerve block (control) or adductor canal block preoperatively after taking baseline measurements of quadriceps strength (quantified by maximum voluntary isometric contraction). The quadriceps muscle strength will be checked 20 minutes after the nerve block to assess strength. All patients will subsequently undergo a general anesthetic. The primary outcome variable will be post-block quadriceps strength as a percentage of baseline from pre-block values. Secondary outcome variables that we will also investigate include: VAS pain score in the post anesthesia recovery unit and post-operative day 1, time to onset of sensory block, duration of nerve blockade, block performance time, patient satisfaction score, perioperative opioid use, perioperative analgesic consumption, incidence of paresthesias, number of needle passes, incidence of post-operative nausea, vomiting, constipation, and any other complications.

Statistical Analysis:

This study is designed as a prospective two-treatment parallel-design study. The primary outcome is quadriceps strength (as measured by maximal voluntary isometric contraction, or MVIC, using a dynamometer). We will obtain baseline measurements of quadriceps strength in the pre-operative phase (pre-block), as well as post-block before surgery. Based on previous research, we assume a reduction in quadriceps strength from baseline of 48% in the adductor canal block group and 82% in the femoral block group. Setting $\alpha = 0.05$ and power = 0.8 we calculated 30 patients per group to show a significant difference with a two-sided test. To adjust for drop out and lost to follow up we increased the sample size by 10% and plan to recruit 33 patients per study group per surgery type (ACL vs. non-ACL arthroscopic surgery). 66 patients will be in the ACL surgery group and 66 patients will be in the non-ACL group. Secondary outcomes will be analyzed separately. Categorical data will be analyzed using Chi-square analysis or Fischer's exact test, depending on sample size. Comparison of means will be performed using the independent sample t-test or the Mann-Whitney U test, depending on distribution. A P-value of 0.05 or smaller will be considered statistically significant.

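### Pain VAS is planned only after surgery and compared without adjustment; a pre-block score used as a covariate could make that valid secondary comparison more precise, by an amount the documents do not fix.

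*Combined protocol and SAP*

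**What the plan says.** Under Study Protocol/Design, pain is a secondary outcome measured at two times, both after the operation: "VAS pain score in the post anesthesia recovery unit and post-operative day 1". The only baseline described is strength. The Statistical Analysis section states: "We will obtain baseline measurements of quadriceps strength in the pre-operative phase (pre-block), as well as post-block before surgery". No pre-block pain score is listed, although nothing says that pain will not be asked.

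For the analysis, the same section says: "Comparison of means will be performed using the independent sample t-test or the Mann-Whitney U test, depending on distribution". Neither test uses a baseline value, and no covariate-adjusted model appears anywhere. The documents give no SD for VAS, no target difference in pain, and no correlation between pain before and after surgery.

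**The concern.** Pain appears in both the brief and the official title, and the rationale is that the adductor canal block spares strength while relieving pain equally well. A strength advantage persuades only if pain is not clearly worse, and that judgement needs a reasonably narrow interval for the pain difference. The trial was not sized for pain, so precision there is whatever the strength calculation happens to leave.

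Patients come to surgery with differing knee pain. If pain before the block predicts pain afterwards, that variation stays in the error term of an unadjusted test. Patients are already assessed before the block for strength, so a score could be taken then. It cannot be recovered later.

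**Working it through.** **Inputs from the documents** (Statistical Analysis section): two-sided test, 5% level, 80% power; 33 patients per arm within each surgery type, hence 66 per arm if the two types are pooled (132 in all). The documents do not make clear whether pain is compared within surgery type or pooled, so both are shown.

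**Input not in the documents:** r, the within-arm correlation of pre-block with post-operative VAS. Assumed range: 0.1 to 0.5.

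**Step 1. The plan's own figure.** The stated 30 per group is reproduced by the two-proportion formula with pooled variance, taking 0.48 and 0.82 as proportions (mean 0.65):

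n = [1.960 × √(2 × 0.65 × 0.35) + 0.842 × √(0.48 × 0.52 + 0.82 × 0.18)]² / 0.34² = 29.7, rounded up to 30.

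This concerns strength only. There is no stated figure for pain to reproduce.

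**Step 2. Unadjusted pain comparison.** For a two-sample t-test the detectable difference is 0.700 SD with 33 per arm and 0.491 SD with 66 per arm. The normal approximation (1.960 + 0.842) × √(2/n) gives 0.690 and 0.488.

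**Step 3. Adjusting for pre-block VAS.** Residual variance is multiplied by 1 − r², so the detectable difference is multiplied by √(1 − r²). The power column takes a difference that the unadjusted test detects with 80% power.

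| r | Variance reduction | Detectable, 33 per arm | Detectable, 66 per arm | Power |
|---|---|---|---|---|
| 0 (unadjusted) | – | 0.70 SD | 0.49 SD | 80% |
| 0.1 | 1% | 0.70 SD | 0.49 SD | 80.4% |
| 0.2 | 4% | 0.69 SD | 0.48 SD | 81.6% |
| 0.3 | 9% | 0.67 SD | 0.47 SD | 83.6% |
| 0.4 | 16% | 0.64 SD | 0.45 SD | 86.4% |
| 0.5 | 25% | 0.61 SD | 0.43 SD | 89.9% |

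**Step 4. Cost of the covariate.** Estimating one more coefficient inflates the variance by about 1 + 1/(2n − 4): 1.016 at 33 per arm and 1.008 at 66. Setting (1 − r²)(1 + 1/(2n − 4)) = 1 gives r² = 1/(2n − 3). Break-even is therefore r = √(1/63) = 0.13 at 33 per arm and r = √(1/129) = 0.09 at 66. At r = 0 the loss is under 2%. At r = 0.5 the net variance ratio is about 0.76 in both cases.

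**Step 5. Why not a change score.** With equal variances, its variance relative to the unadjusted comparison is 2(1 − r): 1.8 at r = 0.1, 1.4 at r = 0.3 and 1.0 at r = 0.5. Below r = 0.5 it is worse than using no baseline at all.

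**The case against.** The strongest reply is that nothing here is an error. VAS is one of many secondary outcomes, the sample size rests on strength, and the unadjusted tests are valid under randomization. This stands: the issue is efficiency only.

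A second reply is that r may be small. Pre-block pain reflects the knee condition, whereas recovery-unit pain follows surgery, general anesthesia, a fresh nerve block and analgesics. If surgery type explains part of the variation in pain, the correlation within type may be smaller still. This also stands, which is why the range starts at 0.1, where the gain is negligible.

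A reader might infer that the pain comparison is biased, or that any chance imbalance in starting pain passes in full into the result. The documents do not support that. The unadjusted standard error already allows for chance imbalance, so this is the same loss of precision described a second time. Only the fraction r carries over: at r = 0.4, an imbalance of 0.5 SD shifts the VAS difference by 0.4 × 0.5 = 0.2 SD. An imbalance that large is uncommon. The SD of the baseline difference is √(2/33) = 0.246 at 33 per arm, so 0.5 SD or more occurs in about 4% of trials; at 66 per arm (SD 0.174) it occurs in about 0.4%.

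A reader might also infer that asking the question is enough to gain precision. It is not, because the planned tests would ignore the answer.

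**Conclusion.** The point holds as a cheap improvement to a secondary analysis. The listed pain comparison is valid but may be less precise than it could be. For an assumed r of 0.1 to 0.5 the gain runs from practically nothing to a 25% cut in residual variance, the latter equivalent to 1/(1 − 0.25) − 1 = 33% more patients. After the cost of the covariate there is no gain below about r = 0.1.

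The conclusion assumes that patients remain to be enrolled, which the documents do not state, and that the score is actually used in the model. A firmer claim, that precision is certainly being lost or that the pain result would mislead, is not supported, because the documents give no value for r. The strength analysis and its sample size are untouched.

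**What to change.** For patients still to be enrolled, record one VAS pain score at the pre-block strength assessment. Prespecify that recovery-unit VAS and day-1 VAS are each compared by a linear model with arm, surgery type and pre-block VAS as terms (without surgery type if the analysis is run within one type). Do not use a change score. Since the plan already provides for non-normal data, name a rank-based version of the same model for use if VAS is markedly skewed.

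The cost is one question, one form field and a short addition to the SAP, with a loss of under 2% in variance if r is near zero. Patients already enrolled will lack the value; keep them in the analysis by mean imputation of the covariate or a missing-baseline indicator. If enrolment is complete, the change brings nothing. Recording pre-operative opioid use at the same visit, as a covariate for the opioid outcome, is an optional addition; the documents offer no basis for putting a size on its benefit.

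### Does the lack of a rule for unobserved sensory onset or block offset undermine the comparison of onset time and block duration?

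*Combined protocol and SAP*

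**What the plan says.** The section Study Protocol/Design lists onset and duration among the secondary outcomes: "time to onset of sensory block, duration of nerve blockade, block performance time". It gives neither a definition nor a schedule for them. Three nearby statements bear on what could be observed:

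- For strength: "The quadriceps muscle strength will be checked 20 minutes after the nerve block to assess strength".
- For anesthesia: "All patients will subsequently undergo a general anesthetic".
- The latest time named for any outcome belongs to pain: "VAS pain score in the post anesthesia recovery unit and post-operative day 1".

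Under Statistical Analysis, the method for continuous outcomes is: "Comparison of means will be performed using the independent sample t-test or the Mann-Whitney U test, depending on distribution". On secondary outcomes the section adds only "Secondary outcomes will be analyzed separately". The significance level is 0.05. There is no rule for censored or missing values. The 10% increase for drop-out affects recruitment, not analysis.

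**The concern.** Both named tests need a value for every patient. A patient whose sensory block has not set in before the general anesthetic may have no onset time, and a patient whose block persists at last contact has no offset time. Three treatments are possible: drop the patient, enter the cut-off as the time, or rank the patient longest. They can give different answers, and the plan does not choose between them.

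Dropping is the most harmful. It removes the longest times, and removes more of them from the arm with more long times. With similar spreads this shrinks a true difference; with unequal spreads it can create, exaggerate or reverse one. At stake would be the description of how quickly each block works and how long it lasts, resting on a choice that could be made after the data are seen.

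**Working it through.** **The plan's own figure.** The only sample-size figure is for the primary outcome. Treating the 48% and 82% as proportions, with two-sided α = 0.05 and power 0.80:

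n = [1.960·√(2 × 0.65 × 0.35) + 0.842·√(0.48 × 0.52 + 0.82 × 0.18)]² / 0.34² = (1.322 + 0.530)² / 0.1156 ≈ 29.7, so 30 per group.

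Adding 10% gives 33. Nothing about onset or duration enters this calculation, so the concern cannot disturb it.

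**Inputs for the concern.** From the documents: 33 per arm within one surgery type, and α = 0.05. The documents give no means, SDs, cut-offs or shares unobserved for onset or duration. Every such input below is an assumption.

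**Formulas.** For a normal time with mean μ and SD σ, a cut-off c, and a = (c − μ)/σ:

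- share unobserved = 1 − Φ(a)
- mean after dropping = μ − σφ(a)/Φ(a)
- mean after capping = μΦ(a) − σφ(a) + c(1 − Φ(a))

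**Case 1: 18 vs 22 h, SD 6, cut-off 24 h.**

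- 18 h arm: a = 1.000, unobserved 15.9%. Dropped mean 18 − 6 × 0.2420/0.8413 = 16.27 h; capped mean 17.50 h.
- 22 h arm: a = 0.333, unobserved 36.9%. Dropped mean 22 − 6 × 0.3774/0.6306 = 18.41 h; capped mean 20.47 h.
- The true 4.0 h becomes 2.1 h dropped and 3.0 h capped.

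The same inputs at later cut-offs (power from about 4,000 simulated trials per setting, so the second decimal varies between runs):

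| Cut-off | Unobserved | Difference, dropped | Difference, capped | t-test power, dropped | Mann-Whitney power, ranked longest |
|---|---|---|---|---|---|
| 24 h | 16% vs 37% | 2.1 h | 3.0 h | 0.37 | 0.72 |
| 30 h | 2% vs 9% | 3.2 h | 3.8 h | 0.64 | 0.73 |
| 36 h | 0.1% vs 1% | 3.9 h | 4.0 h | about 0.75 | 0.73 |
| 48 h | none | 4.0 h | 4.0 h | as complete data | as complete data |

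With complete data, power is about 0.76 for the t-test and 0.73 for Mann-Whitney.

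**Case 2: both means 20 h, SD 3 vs 8, cut-off 24 h.** Dropped means are 20 − 3 × 0.1640/0.9088 = 19.46 h and 20 − 8 × 0.3521/0.6915 = 15.93 h. A true difference of 0 becomes −3.5 h. The t-test after dropping rejects in about 86% of trials; Mann-Whitney with longest ranks rejects in about 6–7%.

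**How robust is longest ranking?** In Case 2 its rejection rate depends on the cut-off: about 6% at 24 h, 18% at 20 h, 41% at 18 h and 69% at 16 h. The test compares distributions, not means. If spreads differ greatly and the cut-off is early, a significant result need not mean a difference in means.

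**Do the documents supply the harmful conditions?** The large effects need a substantial share of unobserved times and an analyst who drops them.

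- The 20-minute check is stated for strength, not sensation.
- Post-operative day 1 is stated for pain, not block offset.
- The general anesthetic could hide a late onset, but it does not end follow-up for duration.
- Nothing says patients are to be dropped.

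**The case for a change.** The strongest case for a change is that the omission is real and closing it would be cheap. Unobserved events are plausible: surgery is ambulatory, every patient is anesthetized after the block, and no contact later than post-operative day 1 is named. The error from dropping is a bias, so more patients do not cure it. With equal durations but observation ending at 24 h in one arm and 30 h in the other, dropping gives false-positive rates of 28–29% at 33 per arm and 52–53% at 66 per arm. A few sentences and two recorded times would settle the handling before the data are seen.

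The omission stands, and so does the arithmetic under its assumptions. What does not stand is the step from a missing rule to a faulty analysis. The severe figures rest on chosen inputs: 37% of an arm unresolved, an SD ratio of nearly three, or observation windows that differ by arm. None has support in the documents.

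The proposed remedy is less clear-cut than it seems. Its preferred test is one the plan already allows, and that test is itself sensitive to the cut-off when spreads differ. Its switch to a log-rank test when contact times vary has no threshold, so it leaves a choice open after the data are seen. With contact times spread over 18–30 h it shows no power gain (0.66 against 0.68 for Mann-Whitney).

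**Conclusion.** No change to the plan is called for. It is silent on what happens when sensory onset or block offset is not observed, but silence is not an instruction to drop patients, and a reasonable analysis is available within the tests it names.

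Under the assumed 18 vs 22 h, SD 6 and 33 per arm, careless handling would cost about half the power (0.76 to 0.37) and 1.9 h of a 4.0 h difference at a 24 h cut-off. At 36 h it would cost about 0.1 h and 0.02 of power or less, and at 48 h nothing. The documents do not show where in this range the trial lies.

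The conclusion assumes that the analyst keeps patients without an observed event, or that such patients are few. If many times prove unobserved and those patients are left out, the published onset and duration comparisons should be read with the bias above in mind. The primary strength comparison and the 30 per group behind it are untouched.

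### The test for continuous outcomes is left to the observed distribution, no effect estimate is named, and the plan does not say whether the two surgery types are compared together or separately; fixing all three costs only wording

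*Combined protocol and SAP*

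**What the plan says.** The Study Protocol/Design section defines a continuous primary outcome: "The primary outcome variable will be post-block quadriceps strength as a percentage of baseline from pre-block values". The Statistical Analysis section then gives one sentence on continuous data: "Comparison of means will be performed using the independent sample t-test or the Mann-Whitney U test, depending on distribution". It states no criterion for the choice and no time at which the choice is made. The sentence comes after the remark that secondary outcomes are handled separately, so it may cover all continuous outcomes or only the secondary ones.

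The only rule for results is "A P-value of 0.05 or smaller will be considered statistically significant". No mean difference, confidence interval or other effect estimate is named.

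On sample size, "we assume a reduction in quadriceps strength from baseline of 48% in the adductor canal block group and 82% in the femoral block group", and from this "we calculated 30 patients per group to show a significant difference with a two-sided test". After a 10% increase, recruitment is set at "33 patients per study group per surgery type (ACL vs. non-ACL arthroscopic surgery"), so that "66 patients will be in the ACL surgery group and 66 patients will be in the non-ACL group". The section does not say whether the primary comparison is pooled, stratified or run in each surgery type, and it gives no success rule across the types.

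**The concern.** A t-test compares means. A Mann-Whitney test compares whole distributions, and it is a test of equal means only under added conditions, such as equal spread and shape in the two arms. If the observed distribution picks the test, the data settle which quantity is compared. Writing down a normality threshold would make the choice reproducible, but the quantity would still depend on the data.

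This matters most where the arms may have similar averages. The Study Protocol/Design section says the adductor canal block has been "purported by small volunteer studies to provide equally effective analgesia", so near-equal average pain or opioid use is plausible. A bare P-value then says little: a non-significant result does not show how similar the arms are, and a significant rank test does not say whether the means differ. An estimate with a confidence interval would help with both.

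The surgery-type gap is separate. Each type is recruited to the full calculated size, so a pooled answer and two separate answers are both consistent with the text, and they carry different error rates.

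**Working it through.** **1. Inputs.** From the Statistical Analysis section: two-sided alpha 0.05, power 0.80, reductions of 48% and 82% (52% and 18% of baseline, a difference of 34 points), 30 per group, 33 after the 10% increase, two surgery types. No SD, CV, distribution or selection criterion is given, so every spread below is an assumption.

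**2. The plan's own figure.** The two-proportion formula with pooled variance under the null, mean proportion 0.65, gives

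n = [1.960·√(2·0.65·0.35) + 0.842·√(0.48·0.52 + 0.82·0.18)]² / 0.34² = 29.7, so 30 per group; 30 × 1.10 = 33.

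The stated 30 is reproduced. A t-test for 34 points also gives 30 per group if the SD is 46.2. The documents do not say which formula was used, so 30 per group does not reveal an SD.

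**3. The switching rule.** The assumed rule is Mann-Whitney if Shapiro-Wilk gives P < 0.05 in either arm, otherwise the t-test. There were 8,000 simulated trials per scenario with equal means in both arms. Entries are rejection rates at 33 and 66 per arm.

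| Assumed data | Rule | Always Mann-Whitney | t / Welch |
|---|---|---|---|
| Opioid dose, gamma, CV 0.8 vs 0.6 | 8.6%, 11.3% | 8.4%, 11.3% | 4.9-5.0% |
| Opioid dose, lognormal, CV 0.8 vs 0.6 | 8.9%, 12.5% | 8.9%, 12.5% | 4.9-5.0% |
| VAS 0-10, SD 2.5 vs 2.0 | 6.7%, 8.1% | 6.6%, 8.1% | 5.2%, 4.5% |
| Percent of baseline, SD 25 vs 18 | 9.1%, 12.0% | 8.7%, 12.0% | 4.8-4.9% |
| Percent of baseline, SD 22 vs 20 | 5.3%, 5.2% | | |
| Equal spreads, all outcomes | 4.5-5.2% | | |

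The rule chose Mann-Whitney in 83-100% of runs, so its results lie within 0.4 point of always using that test. The excess grows with sample size because the rank test is finding a real difference: in the gamma case the medians are 15.9 and 17.7 at a common mean of 20.

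**4. The mirror case.** With the same gamma CVs but equal medians, Welch's test rejects about 7% (33 per arm) and 11% (66 per arm), while Mann-Whitney stays near 5%. Each test is valid for its own question. The fault is in leaving the question open.

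**5. The primary decision.** At 52% versus 18% of baseline with SD 25 and 18, every test considered rejects in essentially all trials.

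**6. Surgery types.** The two types contain different patients, so the tests are independent. If either success counts at 0.05 each, familywise error is 1 − 0.95² = 0.0975; at 0.025 each it is 1 − 0.975² = 0.0494. If both must succeed, 0.05 each is enough. Power for 34 points at SD 30 with 33 per arm is 0.995 in each type and 0.995² = 0.990 for both. It is higher at SD 25, when pooled, or if either type suffices at 0.025.

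**7. The proposed model.** With robust (HC3) standard errors and 10,000 simulated trials at SD 25 vs 18, the model rejects 4.8% (33 per arm) and 4.6% (66 per arm, pooled) at equal means. CI coverage is 95.2-95.4%, and the half-width is about 11.0 and 7.6 points.

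**The case against.** The strongest reply is that the unequal-spread result is not error inflation. It appears only when means are held equal while the distributions differ, and the mirror case turns the same charge against Welch's test. That reply stands. Rank tests are also reasonable for skewed or ordinal outcomes such as satisfaction scores or needle passes. Nor does either test dominate on power: for a 33% lower mean opioid dose at equal CV 0.8 and 33 per arm, Welch against Mann-Whitney is 0.50 against 0.43 for gamma data and 0.53 against 0.60 for lognormal data. So there is no case for a means-based test on every secondary outcome.

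It is also fair that the heading used for the continuous comparison may be loose wording, that a threshold for significance does not mean estimates will be withheld, and that full recruitment within each type may reflect two intended questions. These points soften the criticism, but they do not tell a reader which analysis is planned. If the quoted sentence covers only secondary outcomes, the primary outcome has no named test at all.

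Three stronger readings are tempting and unsupported:

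- A reader might infer that the plan has a false-positive rate of 8-12%. That needs equal means with unequal spreads of an assumed size; with identical distributions the rule is sound.
- A reader might infer a familywise error of 9.75%. That holds only if success in either type counts, which the documents do not say.
- A reader might back-solve an SD of 46.2 (or take 40) and infer that power depends heavily on the success rule. On a 0-100% scale with mean 18, the SD cannot exceed √(18 × 82) = 38.4, and at SD 25-30 power is about 0.99 or higher under every rule.

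**Conclusion.** The concern holds as a gap in specification, and closing it is a cheap improvement. Three things are open in the text: which test, and so which quantity, is used for continuous outcomes; what effect estimate accompanies the P-value; and whether the surgery types are compared together or separately.

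The consequence is limited. The primary conclusion is safe if the assumed effect is near the truth. For outcomes with similar means, the choice of test could change the answer if spreads differ materially (about 7-12% rejection in the larger assumed differences, about 5% in the mildest one). Those figures rest on assumed spreads and an assumed selection rule; they show direction and do not estimate this trial's error rate. The 9.75% figure is exact, but conditional on an either-type success rule.

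**What to change.** **Primary outcome.** Fix the analysis in advance as a linear model of post-block MVIC as a percentage of baseline on arm, baseline MVIC and surgery type, pooled over both types, with heteroscedasticity-robust standard errors. Report the mean difference with 95% CI and P-value. Give within-type estimates and CIs as supportive.

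**If separate answers by type are intended,** say so, and state whether both must succeed (each at 0.05) or either suffices (each at 0.025).

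**Continuous secondary outcomes.** Name one test per outcome in advance, whatever distribution is observed, and report a matching effect estimate with CI. A rank test is acceptable for skewed or ordinal outcomes if it is described as a comparison of distributions.

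**Cost.** SAP wording only, with no added patients or data. The downside is slightly more analysis and presentation work. No precision gain is claimed for the baseline term.
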